The proposed study is a single-arm clinical trial to generate pilot data regarding the safety, feasibility and efficacy of an exercise intervention. Participants will complete a baseline assessment (Visits 1A +/- 1B) at 0 weeks followed by up to 12 weeks of HIIT intervention followed by a repeat assessment (Visits 2A +/- 2B). An overview of the study protocol is provided in Figure 1.

Figure 1: Protocol Overview

Visits 1A/1B and 2A/2B: Visits 1A and 2A will be performed in the inpatient unit of the Clinical and Translational Research Center at the University of Colorado. Each visit will include administration of SF-36 questionnaire, spirometry, and a cardiopulmonary exercise test. Peripheral IV will be placed for the purpose of venous blood draws for complete blood count, ferritin and untargeted metabolomics analysis.(1) Radial arterial line will be placed for continuous blood pressure monitoring and measurement of arterial blood gas and lactate. Participants will be oriented to VO2max testing protocol. Baseline fitness will be assessed by questioning to determine step protocol. Once arterial line is in place, participants will complete a symptom-limited CPET on an upright stationary bicycle. Workload will begin at 0 Watts and increase every minute by 10-30 W (based upon pre-testing questioning) to achieve volitional exhaustion with maximum workload at 8-12 minutes.(22) Heart rate and rhythm, blood pressure, oxygen saturation, and gas exchange parameters (VO2, VCO2, and minute ventilation) will be continuously measured. Borg RPE, arterial blood gas and lactic acid will be measured at rest, every 4 minutes during exercise, and at peak exertion. Attainment of a high-quality VO2max will be determined based upon achieving one or more of the following: a plateau in VO2; attainment of predicted VO2max, work rate, or heart rate; respiratory exchange ratio >1.15, and Borg Scale rating 9-10 on a 0-10 scale.(6) Peripheral venous blood draw for untargeted metabolomics analysis will be repeated at peak exercise.

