Peripheral venous blood sample collection: Peripheral venous blood samples will be collected during Visits 1A and 2A. Samples will be collected from the peripheral IV. Five samples of 3-5 cc each will be collected at rest and two samples of 3-5 cc each will be collected after maximal exercise (a total of 7 samples = 21-35 cc blood). One sample from rest will be used to obtain a complete blood count and ferritin. One sample from each timepoint will be saved for storage in a -80° C freezer accessible to the study investigators in University of Colorado Research Complex Building 2 for future analyses. The other two samples will be processed via 2000 g centrifuge for 10

minutes at 4° C. Plasma and red blood cells will be isolated into separate tubes prior to storage in the same -80° C freezer. The plasma and RBC samples will be transported later to the University of Colorado School of Medicine Metabolomics Core lab. Metabolomic assessment will be performed using Vanquish ultra-high-performance liquid chromatography coupled to Q Exactive mass spectrometry (UHPLC-MS; Thermo Fisher Scientific, San Jose, CA, United States). Additionally, two samples will be used for isolation of monocytes/macrophages (one will be placed in an EDTA tube for separation into red blood cells, monocytes/macrophages, and plasma and one in an untreated tube for plasma; both will be separated via a Ficoll gradient technique and resuspended in RPMI media). Risks of peripheral venous blood sample collection include pain and bleeding.

Echocardiography: Transthoracic echocardiography may be utilized in Visits 1B and 2B to collect information on right and left ventricular function at rest and immediately after peak exercise. It is possible that participants may feel slight discomfort from a probe sitting over the skin.

COVID-19 rapid antigen testing: According to outpatient CTRC facility guidelines, immediately prior to Visits 1B and 2B participants may be asked to perform a COVID-19 rapid antigen test. If positive, the visit will be terminated and rescheduled. Participants will self-administer COVID-19 test by gently inserting a cotton swab into both nares. Risks include discomfort or inconvenience at identifying asymptomatic COVID-19 infection.

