Recruitment of participants: This pilot study seeks to study 12 individuals in a one-year timeframe. [name], a PI and an expert in deployment-related respiratory disease,(11, 29-31) is the director of the Rocky Mountain Regional Post Deployment Cardiopulmonary Evaluation Network. Her presence lends feasibility to this proposal's participant recruitment. With >200 patients enrolled in research initiatives through the RMR PDCEN and Chest Exposure Clinic and based on the research team's experience recruiting for similar exercise assessment protocols (COMIRB #16-1635, 17-1042, 19-1141, 21-4354),(8, 32, 33) a sample size of 12 is feasible to recruit and study in one year.

Heterogeneity of study population: Deployment-related respiratory disease is by nature a heterogeneous condition. While narrowing the study population to a particular pathophysiologic subgroup might strengthen the study's conclusions, for the purpose of collecting pilot data in the specified one-year timeframe this study will include individuals with multiple phenotypes (i.e. distal lung disease, asthma and unexplained dyspnea; see "Inclusion Criteria"). However, to minimize additional heterogeneity participants will be carefully screened and excluded for comorbid conditions (see "Exclusion Criteria"). Additionally, a heterogenous BMI range is included again for the purpose of collecting pilot data in the specified one-year timeframe. BMI will be tested as a covariate in the statistical analysis, and based upon these analyses future studies may be designed with a more narrow BMI inclusion range.

Lack of control group: The lack of a control group will limit conclusions regarding efficacy of HIIT intervention. However, for the purpose of collecting pilot data in the proposed timeframe this is felt to be appropriate. This study will instead inform future larger randomized controlled trials of exercise interventions in this population.

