Hypothesis 1B: Increased right ventricular afterload causes maladaptive right ventricular remodeling which is reflected by increased glycolytic metabolites (compared to a reference healthy population).(2, 3) Metabolomics partial least squares discriminant analysis and t-test or ANOVA will be performed. Exercise metabolomics data collected in a healthy population (COMIRB 21-4354) will be used as a reference.

Hypothesis 1C: Impaired right ventricular performance contributes to reduced maximum oxygen consumption (VO2max) relative to healthy population norms, dyspnea and impaired health-related quality of life. VO2max will be analyzed using descriptive statistics and presented in reference to healthy population norms (ATS/ACCP guidelines).(6) Dyspnea and health-related quality of life will be assessed by SF-36 with scores analyzed by descriptive statistics. Scores will be presented in

reference to disease population references.(34, 35) Linear mixed models will be used to assess the relationship between impaired right ventricular performance as measured by pulmonary artery systolic pressure and VO2max. Covariates including BMI, gender, age and type of deployment-related respiratory disease will be included.

Specific Aim 2:

Hypothesis 2A: *HIIT is safe and feasible among military personnel suffering from deployment-related respiratory disease, with $\geq 80\%$ participation in prescribed sessions.*(8) Attendance will be calculated as (number of supervised sessions attended + unsupervised sessions reported by exercise diary) / total number of supervised + unsupervised sessions. Feasibility will be based upon attendance of $>80\%$ of prescribed exercise sessions, with separate analyses for HIIT sessions, “light exercise” sessions, and combined sessions. Safety/acceptability will be based upon an absence of major adverse events attributable to the exercise training program and $<5\%$ minor adverse events (calculated as the number of adverse events divided by the total number of exercise sessions throughout the program) attributable to the exercise training program.

Hypothesis 2B: *Participants will spend approximately 4.5 hours/week engaged in this program and will report that participation was feasible.* Total hours spent in exercise program will be calculated based upon number of supervised sessions and reported unsupervised sessions. Qualitative assessment of feasibility will be collected via narrative report.

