Hypothesis 2C: *Staff will spend approximately 2 hours/participant in exercise supervision and coordination. Staff will report that level of supervision and time commitment was appropriate and feasible.* Staff time spent in exercise supervision will be calculated by [hours spent supervising exercise / number of individuals supervised simultaneously + hours spent scheduling and/or coordinating]. Staff's qualitative assessment of feasibility will be collected via narrative report.

Specific Aim 3:

Hypothesis 3A: *HIIT induces positive right ventricular and pulmonary vascular remodeling, improving right ventricular performance and exertional cardiac output, reflected by decreased glycolytic metabolites on peripheral venous metabolomics; improved exertional pulmonary artery systolic pressure on TTE; and improved oxygen pulse, ventilatory efficiency, and dead space fraction on CPET. Additionally, markers of left ventricular diastolic function on TTE will improve reflecting general positive training adaptations of HIIT.*(8) Metabolomics heat maps, partial least squares discriminant analysis, and t-test or ANOVA will be performed to compare pre- vs post-exercise training glycolytic metabolites. Pulmonary artery systolic pressure on TTE and oxygen pulse, ventilatory efficiency, and dead space fraction on CPET will be analyzed using descriptive statistics and compared pre- and post-exercise program by t-test. Resting left ventricular diastolic function (E/e') will be analyzed using descriptive statistics and compared pre- and post-exercise training by t-test.

Hypothesis 3B: *HIIT improves VO2max among patients with deployment-related respiratory disease.* VO2max will be analyzed using descriptive statistics and compared pre- and post-exercise training by t-test.

Hypothesis 3C: *HIIT improves dyspnea and health-related quality of life (SF-36).* SF-36 pre- and post-exercise training will be analyzed using descriptive statistics and compared pre- and post-exercise training by t-test.

Results will be analyzed according to an intention-to-treat protocol. A p-value of <0.05 will be used to establish statistical significance. Statistical analysis will be performed using SAS v 9.4 (SAS Institute Inc., Cary, NC, USA). For metabolomics data, the MetaboAnalyst 4.0 package will be used for analysis and XY graphs will be created using GraphPad Prism 8 (GraphPad Software Inc., La Jolla, CA, United States).

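### For the 1B and 3A metabolomics the only stated significance rule is p<0.05; false-discovery control, PLS-DA validation, metabolite list, matrix and time point are not stated.

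*Combined protocol and SAP*

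**What the plan says.** Under Outcome Measures, untargeted metabolomics of peripheral venous blood is a secondary outcome.

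The Data Analysis Plan gives the methods. For Hypothesis 1B: "Metabolomics partial least squares discriminant analysis and t-test or ANOVA will be performed", followed by "Exercise metabolomics data collected in a healthy population (COMIRB 21-4354) will be used as a reference". For Hypothesis 3A: "Metabolomics heat maps, partial least squares discriminant analysis, and t-test or ANOVA will be performed to compare pre- vs post-exercise training glycolytic metabolites". The closing paragraph of that section adds "A p-value of <0.05 will be used to establish statistical significance" for all results, and "For metabolomics data, the MetaboAnalyst 4.0 package will be used for analysis", with no settings.

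The samples are described elsewhere. Study Design and Research Methods says of Visits 1A and 2A: "Peripheral venous blood draw for untargeted metabolomics analysis will be repeated at peak exercise". The section on peripheral venous blood sample collection separates plasma from red cells and says "The plasma and RBC samples will be transported later to the University of Colorado School of Medicine Metabolomics Core lab". Its count is seven tubes per visit: one for blood count and ferritin, two stored (one per time point), two for monocyte work, and two spun for metabolomics (one per time point). Each visit therefore yields 2 matrices x 2 time points = 4 metabolomics data sets.

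**The concern.** Hypotheses 1B and 3A treat glycolytic metabolites as the blood marker of maladaptive right ventricular remodeling and of its reversal by training. The plan states a direction for each (increased in 1B, decreased in 3A). It does not say which metabolites are meant, which of the four data sets carries the test, how many must move, or how the p-values are handled together. These choices can therefore be made after the data are seen, with p<0.05 as the only stated bar.

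PLS-DA adds a second problem. It builds its components to separate the labelled groups, so with few people and many features it separates them even when nothing differs. Without cross-validation or permutation, a clean score plot is weak evidence. Since the pilot is meant to inform a larger study of mechanism, a chance finding could be carried forward.

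**Working it through.** **Plan's own figure.** The documents give no metabolite count, power or error rate for metabolomics. Their one sample-size calculation concerns VO2max and does not bear on this point.

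**Inputs from the documents.** n=12 (a ceiling: up to 12 are to be enrolled); p<0.05; four data sets per visit.

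**Assumed.** 5-10 glycolytic metabolites; two-sided tests, since sidedness is not stated; only hits in the hypothesised direction count, so the rate per test is 0.05/2 = 0.025.

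**1. False hits, independent tests.** For m tests:

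- At least one: 1 - 0.975^m. One data set, m=5 or 10: 0.119 or 0.224. Four data sets, m=20 or 40: 0.397 or 0.637.
- At least two: 1 - 0.975^m - m x 0.025 x 0.975^(m-1). For m=5, 10, 20, 40: 0.006, 0.025, 0.088, 0.264.

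**2. Correlated tests.** Paired t-tests at n=12 were simulated, 20,000 runs, with the same correlation between metabolites and between data sets for the same metabolite. Each cell gives 5 / 10 metabolites.

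| Correlation | One set, at least 1 hit | Four sets, at least 1 hit | One set, at least 2 hits | Four sets, at least 2 hits |
|---|---|---|---|---|
| 0 (formula) | 12% / 22% | 40% / 64% | 0.6% / 2.5% | 9% / 26% |
| 0.5 | 10% / 15% | 27% / 39% | 2.5% / 5% | 11% / 22% |
| 0.8 | 7% / 9% | 15% / 20% | 3% / 5% | 9% / 14% |

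The 0.5 one-set figure for five metabolites is 9-10% within simulation error. Only the shortest list at the strongest correlation falls below 9%. A two-sample t-test, as in 1B, has the same 2.5% rate per test in one direction.

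**3. With Benjamini-Hochberg at 5%** on the same simulated data (correlation 0 and 0.5), any false hit in the hypothesised direction occurs in 2.2-2.7% of runs, for one set or four.

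**4. PLS-DA on pure noise, two components.**

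- 1B, 12 reference subjects assumed because the plan gives no number. With 10 features, in-sample accuracy is 77-79%, against about 49% cross-validated. With 100-150 features it is 99-100%, against 46-48% by leave-one-out.
- Varying the reference group from 8 to 30 subjects at 100 features gives 97-100% in-sample.
- 3A, 12 people measured twice (pre/post correlation 0.5), 5-10 metabolites: 63-72% in-sample, against 50% with each person left out whole. None of 1,000 data sets separated perfectly.

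**5. Power cost.** At n=12 an unadjusted paired t-test has 80% power for a change of 0.89 SD. Under Benjamini-Hochberg, power per metabolite at that change is 73-76% if all 5-10 listed metabolites change, 60-67% if about half do, and 40-53% if only one does.

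**The case against.** The strongest reply is that no rule makes a single hit count as support. Both hypotheses speak of glycolytic metabolites as a class, and 3A adds heat maps and PLS-DA, which suggests reading a pattern. This stands: the false-hit figures are conditional, and with two hits required one data set gives only about 1-5%. Testing all four sets would still leave 9-26%, though the plan does not commit to testing all four.

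Second, this is a secondary outcome in a 12-person pilot. Aim 1 is framed as generating hypotheses, Aim 3 as pilot data, and no decision rule depends on the metabolomics. Reporting unadjusted p-values labelled exploratory would be defensible. That limits the severity, but the plan does apply p<0.05 to declare significance and does not give the metabolomics that label at the point of analysis.

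Three stronger readings are tempting and not supported:

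- **That the plan rules out false-discovery control or validation.** It names software without settings, so these steps are neither stated nor excluded.
- **That hundreds of untargeted features will be screened at 5%, or that noise will separate perfectly in both analyses.** Both hypotheses concern glycolytic metabolites. In 3A the methods sentence itself is confined to them, and noise there gives 63-72%, not perfect separation. The near-perfect figure for 1B applies only if the whole panel is modelled, which its methods sentence leaves open.
- **That the 1B comparison is invalid because the reference subjects come from a separate protocol.** That is a question of comparability, which neither false-discovery control nor cross-validation addresses. The documents list the reference protocol among the team's similar exercise protocols and do not describe its samples well enough to judge.

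The lack of the word paired in 3A is a matter of clarity only, since the same participants are measured before and after.

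**Conclusion.** The point holds as an omission with a measurable effect. That these items are not stated is certain from the text; the size of the effect is not, because metabolite count, correlation, reference-group size and the rule for support are all assumed. Under the any-one-hit reading the nominal 2.5% rises several-fold in one data set, and further if all four are searched. Unvalidated PLS-DA is moderately optimistic for a short glycolytic list and uninformative for a whole panel. Fewer than 12 completers would lower power but leave the false-hit rates essentially unchanged. The matter is worth fixing, but it does not touch the primary outcomes.

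**What to change.** Before the metabolomics data are seen, add to the Data Analysis Plan:

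1. A list of the glycolytic metabolites, and one main matrix and time point for each of 1B and 3A.
2. Benjamini-Hochberg applied to that list, with unadjusted p-values shown alongside. All other metabolites, matrices and time points are reported as exploratory.
3. PLS-DA reported only with cross-validated Q2 and a permutation p-value. For 3A, keep each person's samples together in the same fold and permute within person.

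This needs plan wording and a little analysis time, with no new visits or samples. The real cost is the loss of power per metabolite shown above, largest when only one listed metabolite changes. Keeping the list short limits it, and showing unadjusted p-values lets readers see leads that miss the adjusted threshold.

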- Adverse events (recorded at supervised exercise sessions or reported from home sessions)
- Time commitment per participant (for participants, calculated as sum of hours exercising; for staff, calculated as [hours spent supervising exercise / number of individuals supervised simultaneously + hours spent scheduling and/or coordinating for that participant])
- Qualitative feasibility collected via narrative survey of participants and staff

B. Description of Population to be Enrolled:

Men and women ages 18-65 with deployment-related respiratory disease and symptoms of exertional dyspnea or exercise intolerance residing in the Veterans Integrated Service Network (VISN) 19 and receiving some or all of their care at VA medical facilities throughout the Eastern Colorado Health Care System (ECHCS) will be recruited. We will enroll up to 12 eligible veterans.

- **Inclusion Criteria:**

- Deployment of ≥ 30 days to Iraq, Afghanistan, Kuwait, Saudi Arabia, Bahrain, Qatar, United Arab Emirates, Kyrgyzstan, or Djibouti after September 2001(11)
- New onset of cough, shortness of breath, chest tightness/wheezing, dyspnea on exertion or exercise intolerance which started during or after deployment(11)
- Definite or probable distal lung disease (≥ 1 hyperinflation, emphysema, bronchiolitis, small airways inflammation, peribronchiolar fibrosis, or granulomatous pneumonitis on surgical lung biopsy; or ≥ 2 centrilobular nodularity, air trapping, mosaicism, or bronchial wall thickening on chest CT),(11) definite or probable deployment-related asthma (≥ 1 increase in post-bronchodilator forced expiratory volume in 1 second [FEV₁] $\geq 12\%$ and ≥ 200 cc, or methacholine challenge with PC₂₀ FEV₁ ≤ 16 mg/mL)(11) or unexplained dyspnea on exertion or exercise intolerance despite noninvasive testing including pulmonary function testing, methacholine challenge, transthoracic echocardiography, and/or chest computed tomography(9, 13)
- Current symptoms of dyspnea on exertion or exercise intolerance
- Residence <90 miles from RMR VA and ability / willingness to attend in-person HIIT sessions and research visits

- **Exclusion criteria:**

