- Active / uncontrolled cardiovascular or pulmonary disease (e.g. hypertension with blood pressure $>160/100$ despite antihypertensive therapy, known hypertensive response to exercise [systolic blood pressure >220 mmHg in men / >190 mmHg in women], coronary artery disease, left ventricular ejection fraction $\leq 45\%$ or heart failure with preserved ejection fraction with ongoing symptoms despite diuretic therapy, uncontrolled arrhythmia, moderate or severe valvular abnormality, diabetes with HbA_{1c} $>8.5\%$ documented within the prior year, chronic obstructive

[figure not shown]
- pulmonary disease or asthma exacerbation requiring steroids within 4 weeks of enrollment, , interstitial lung disease, untreated severe obstructive sleep apnea)
- Pre-deployment history of cardiovascular or pulmonary disease including coronary artery disease, left ventricular ejection fraction $\leq 45\%$ or heart failure with preserved ejection fraction requiring diuretic therapy, arrhythmia, valvular abnormality, chronic obstructive pulmonary disease, asthma (excluding childhood asthma that did not persist into adulthood), interstitial lung disease, or pulmonary hypertension
- Body mass index <18.5 or $>45 \text{ kg/m}^2$
- Anemia with hemoglobin $<10 \text{ g/dl}$
- Disorders that adversely influence exercise ability or ability to complete CPET and HIIT intervention using an upright stationary bicycle (e.g. arthritis or peripheral vascular disease)
- Current fitness program (e.g. >30 minutes at METs >6 3 times/week or more or >90 minutes spent at METs $>6/\text{week}$)(8)
- Pregnancy or possible anticipated pregnancy during study duration
- Breastfeeding status
- Respiratory symptoms determined to be due to alternative cause, including long COVID

Potential participants evaluated at the recruitment sites typically undergo significant evaluation for respiratory symptoms to exclude causes unrelated to deployment-related respiratory disease, increasing the feasibility of applying the exclusion criteria. Additionally, participants may be excluded at the discretion of Principal Investigators (PIs Drs. [name], [name] and [name]) if any conditions are discovered during screening that may increase risk of study participation.

C. Study Design and Research Methods

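### Hypothesis 1B compares patients with an external healthy group by t-test or ANOVA and specifies no matching or adjustment for age, sex or BMI, so a difference in these could be read as right ventricular remodeling.

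*Combined protocol and SAP*

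**What the plan says.** Hypothesis 1B (Data Analysis Plan, Specific Aim 1) holds that raised right ventricular afterload causes maladaptive remodeling, "reflected by increased glycolytic metabolites (compared to a reference healthy population". Two sentences give the analysis: "Metabolomics partial least squares discriminant analysis and t-test or ANOVA will be performed", and "Exercise metabolomics data collected in a healthy population (COMIRB 21-4354) will be used as a reference". Neither mentions matching, restriction or a covariate. The size, age, sex and BMI of the COMIRB 21-4354 group appear nowhere in the document. Potential Scientific Problems lists that protocol among the team's similar exercise assessment protocols, and that is the only other description.

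Two other places bear on adjustment:

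- For Hypothesis 1C, after naming a linear mixed model relating pulmonary artery systolic pressure to VO2max, the plan says "Covariates including BMI, gender, age and type of deployment-related respiratory disease will be included".
- Under heterogeneity of the study population, the protocol notes its wide BMI range and says "BMI will be tested as a covariate in the statistical analysis". No hypothesis or model is named there.

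The patients are "Men and women ages 18-65 with deployment-related respiratory disease". Eligibility allows BMI from 18.5 to 45 kg/m² and excludes people in a current fitness program. The Data Analysis Plan sets significance at p < 0.05 without exempting 1B, and assigns metabolomics to MetaboAnalyst 4.0.

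**The concern.** 1B is the one comparison in Aim 1 that sets patients against individual-level data from another group. Hypotheses 1A and 1C refer to published norms or disease references. The comparison is not randomised, so any characteristic that differs between the groups and is related to the metabolites enters the estimated difference. A t-test or one-way ANOVA cannot separate it out. Processing both sets of samples together would not help, because the difference lies in the people and not in the assay.

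The hypothesis attributes a difference to right ventricular remodeling, and the results are meant to inform larger studies of mechanism. A signal produced by body size or age could point that work in the wrong direction. A real signal could equally be masked. The plan adjusts for these variables in the next hypothesis, so the authors already regard them as relevant.

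**Working it through.** **Figures in the plan.** None is given for 1B. The only sample-size calculation concerns the change in VO2max after training and has no bearing here. What follows is therefore an illustration and not a check of a stated number.

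**Inputs.** From the document: up to 12 patients; threshold 0.05 (sidedness not stated, taken as two-sided). Assumed, because the document gives no reference-group data: n₂ = 12 or 20 controls; no disease effect; within-group metabolite-BMI correlation r = 0.2 to 0.4; mean BMI D standard deviations higher in patients, with D = 0.5, 1 or 1.5.

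**Formula.** With no disease effect the metabolite means differ by r × D standard deviations. The t statistic is then approximately noncentral t with 12 + n₂ − 2 = 10 + n₂ degrees of freedom and noncentrality r × D × √(12 n₂ / (12 + n₂)). A false increase is rejection in the upper tail at the two-sided 0.05 critical value. With balanced groups its probability is 2.5%.

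**Worked case.** For n₂ = 12, √(144/24) = 2.449. With D = 1 and r = 0.2 the noncentrality is 0.490; with r = 0.4 it is 0.980. On 22 degrees of freedom the critical value is 2.074, and the upper-tail probabilities are 6.8% and 15.3%. For n₂ = 20, √(240/32) = 2.739. The noncentralities are 0.548 and 1.095, the critical value on 30 degrees of freedom is 2.042, and the probabilities are 7.6% and 18.4%.

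| BMI gap (D) | 12 controls, r = 0.2 to 0.4 | 20 controls, r = 0.2 to 0.4 |
|---|---|---|
| 0.5 SD | 4.2% to 6.8% | 4.5% to 7.6% |
| 1 SD | 6.8% to 15.3% | 7.6% to 18.4% |
| 1.5 SD | 10.4% to 29.0% | 12.2% to 35.6% |

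**Opposite direction.** If patients were 1 SD lower in BMI, the same formula gives a false increase in at most 0.8% of cases. A true increase would then be understated by 0.2 to 0.4 SD.

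**Does adjustment work?** A separate simulation (20,000 replicates per setting, no disease effect, r = 0.3 or 0.5, 12 or 24 controls) counted rejections in either direction. At a 1 SD gap the unadjusted t-test rejected in 11% to 22% of cases with 12 controls and 13% to 28% with 24. Analysis of covariance on the one covariate returned the rate to about 5% in every setting. With no imbalance the unadjusted test was also at about 5%.

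**Precision cost.** With p the share of patients in the combined sample, adjusting for one covariate with a within-group gap of D inflates the variance of the group effect by about 1 + p(1 − p)D². With 12 per group, p(1 − p) = 0.25. This gives 1.25 at D = 1 and 1 + 0.25 × 2.25 = 1.56, about 1.6, at D = 1.5. Age and sex may add to this.

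**The case against.** The strongest reply starts from what the documents do not show. They are silent on matching; they do not rule it out. A reader might infer that the reference group is known to be unmatched, or that the patients are heavier or older than it. Neither is supported: COMIRB 21-4354 is described only as a healthy population in a similar exercise protocol, and the patients' own eligibility range is wide in both directions. Every input to the illustration except the 12 patients and the 0.05 threshold is assumed, including the sign of the imbalance and the link between glycolytic metabolites and BMI. All of this stands, and it limits the point to what could happen if the groups differ.

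The protocol also states that BMI will be tested as a covariate, so it would be wrong to say BMI is overlooked. That sentence, however, addresses the spread among trial participants, names no model, and leaves out age and sex. The tests named for 1B take no covariate.

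Finally, Aim 1 is meant to generate hypotheses, metabolomics is a secondary outcome, and 1B decides neither a primary outcome nor the safety and feasibility criteria. That lowers the weight. It does not remove the point, since 1B applies formal tests and attributes a difference to a specific mechanism. The protocol's admission that it lacks a control group concerns the efficacy of training, not 1B.

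**Conclusion.** The point holds in conditional form. The plan names an unadjusted comparison with an undescribed external group, and specifies no matching or adjustment for age, sex or BMI in 1B. If the groups differ on variables related to the metabolites, the result cannot be attributed to right ventricular remodeling.

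Under the assumed 1 SD excess in BMI and correlations of 0.2 to 0.4, a false increase occurs in about 7% to 18% of tests per metabolite instead of 2.5%. At half that gap the figure is about 4% to 8%. The reader should not take these as the trial's error rates: the true imbalance, its direction and the correlations are unknown, and with balanced groups there is no inflation. This is a change the plan should make, of modest weight in a hypothesis-generating aim.

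**What to change.** In the Hypothesis 1B paragraph:

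- For the glycolytic metabolites, replace the t-test or ANOVA with a linear model of group plus age, sex and BMI. Alternatively, use COMIRB 21-4354 participants frequency-matched on these, if the data allow.
- Fit the model in SAS, or in another package that takes covariates, and say so, because the plan currently assigns metabolomics to MetaboAnalyst.
- Describe how the reference participants are chosen, and tabulate both groups' age, sex and BMI beside the result.
- Label the partial least squares discriminant analysis as descriptive, since it does not separate group from these covariates.
- If the groups do not overlap on age or BMI, report 1B descriptively only.
- Word any difference as an association. Fitness and exercise workload may still differ: current exercisers are excluded from the patient group, and samples are also drawn at peak exercise.

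The text change is a few sentences. The statistical cost is three degrees of freedom plus the loss of precision from overlap between group and covariates: a variance factor of about 1.25 at a 1 SD BMI gap and 1.6 at 1.5 SD with 12 controls, from BMI alone. The fix also depends on age, sex and BMI being available for the COMIRB 21-4354 participants, which the document does not confirm.
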